5.5 Concomitant medications

At the screening visit (Visit 1), the Investigator will instruct the subjects on the list of permitted and non-permitted concomitant medications.

All concomitant medications taken for any reason (including those taken in the last week prior to entry in the investigation) must be recorded in the appropriate section of the CRF.

5.5.1 Permitted concomitant medications

With the exception of those products listed among non-permitted medications, participants will be allowed to use any concomitant medication (necessary for the treatment of pre-existing concomitant pathologies or for intercurrent diseases), that do not interfere with the investigation evaluation parameters.

5.5.2 Non-permitted concomitant medications and treatments; lifestyle

Chemical (drugs, medical devices, homeopathics, cosmetics, peeling etc.) and/or physical (for example laser or massage) topical treatments at the the injections site are not admitted from visit 1 to final visit. Subjects will be warned to avoid the prolonged exposure to strong sunlight and to tanning lamps in the same time lapse.

5.6 Treatment compliance

Treatment with the investigational devices will be performed at the investigational site under direct control of the treating Investigator, who will ensure correctness of the procedures.

5.7 Investigational medical device storage and accountability

After receipt of the investigational medical device supplies, the Investigator, his/her deputy or the Pharmacist will conduct an inventory and subsequently fill-in and sign the investigational medical devices Delivery Form. The Investigator, his/her deputy or the Pharmacist, will keep investigational medical devices inventory and accountability records.

The required storage conditions will be rigorously followed: protect from damage, freezing and sunlight; store at a temperature between $+ 4^{\circ}$ C and 27° .

The Investigator will keep the investigational medical device in a pharmacy or a locked and secure storage facility, accessible only to those individuals authorised by the Investigator himself.

At the conclusion of the investigation, a final investigational medical devices inventory will be performed and the used and unused investigational medical device will be sent to the Sponsor or locally destroyed at the investigational study site following the completion of an appropriate form, which will be signed by the Investigator or his/her deputy or by the Pharmacist. If any supplies are missing, this must be indicated together with an explanation for the discrepancy.

5.8 Overdosage

Cases of overdosage with the investigational or the reference medical devices are not known. Moreover, in this investigation no investigational device will be left to the subjects hands and hence any risk of overdose is excluded.

6. INVESTIGATIONAL PLAN

The investigational plan will include 4 visits in total at the investigational site: visit 1 (screening and treatment); follow-up Visits 2 (after 2 weeks), Visit 3 (after 12 weeks), Visit 4 (after 24 weeks).

It is recommended that, throughout the entire investigational period, the visits on site will be performed in the morning at approximately the same time of the day for each subject. A 2 day or 10-day flexibility with respect to the scheduled date of the visit is allowed for the planned day of visit 2 and visit 3 and 4, respectively.

The investigational plan and scheduled examinations and procedures are summarised in the following schedule.

	Screening (and treatment) visit	intermediate follow –up visits		Final visit* End of the study	
			I		
Visit	1	2	3	4	
Day	1	14	84	168	
Week		2	12	24	
Written informed consent	Х				
Demographic data	Х				
Medical history	Х				
Physical examination	Х				
Prior and concomitant treatments ¹	Х	X	Х	Х	
Vital signs ²	Х	Х	Х	Х	
Urine pregnancy test ³	Х				
Inclusion/exclusion criteria	Х				
Randomization	Х				
Treatment	Х				
Pain assessment	Х				
GAIS		Х	Х	Х	
WSRS	Х		Х	Х	
Digital photo	Х	Х	Х	Х	
Global investigator assessment				Х	
Global subject assessment				X	
Adverse events ⁴	X	X	X	X	
Investigational device accountability	X				
Investigational device reconciliation				X	

Investigation schedule

*Or Early termination visit in case of investigation discontinuation

¹All concomitant medications taken by the subject (including those taken in the prior week) will have to be recorded in the medical records and in the CRF

²Vital signs will include measurement of blood pressure and heart rate at each visit; height and weight at screening only

³ An urine pregnancy test will be performed in female subjects of childbearing potential (i.e., not permanently sterilised - post hysterectomy or tubal ligation status – or not postmenopausal from at least one year)

⁴Adverse events will be recorded from the obtainment of the Informed Consent form up to the end of the investigation

6.1 Investigation schedule, visits plan and procedures

Visit 1 (Day 1): Screening visit/treatment

Potential participants will be informed orally and in writing about the scope of the investigation, the relevant procedures, the nature of the risks related to the investigation, and they will be asked to sign and date the Written Informed Consent form.

After the correct obtaining of the Informed Consent form, the following assessments and procedures will be performed:

- Demographic data (age, gender, race) will be recorded;
- General medical history will be recorded;
- A general physical examination will be performed, including the measurement of height and weight. Any abnormality identified at the screening visit (Visit 1) should be recorded in the subject's medical records and in the CRF;
- All concomitant medications taken by the subject (including those taken in the prior one week) will be recorded in the subject's medical records and in the appropriate section of the CRF;
- Vital signs (blood pressure and heart rate) will be measured and recorded;
- An urine pregnancy test will be performed in female subjects of childbearing potential (i.e., not permanently sterilised post hysterectomy or tubal ligation status or not postmenopausal from at least one year);
- The digital photo will be done;
- The WSRS will be done;
- Eligible subjects will be included in the investigation and treatments will be done. HAL will be injected on the one side of the face, HA on the other side –by the Treating Investigator . Treatment procedure:
 - 1. Check the randomization list for the type of product (HAL or HA) to be injected in the **RIGHT** side of the face;
 - 2. Take the selected product box;
 - 3. Write the subject number and the date of admnistration on the label;
 - 4. Open the box and pick-up the siringe;
 - 5. Detach the flag label and stick it on the appropriate space present in the CRF (label not available in consequence of whatever reason, a withness will write the product code –HA or HAL- in the space, dating and signing it);
 - 6. Disinfect the skin thoroughly with iodopovidone or chlorhexidine disinfectant.;
 - 7. Screw the needle firmly onto the luer-lock connection of the syringe;
 - 8. Press gently on the plunger in order to expel any residual air from the device;
 - 9. If the needle is obstructed, do not increase pressure on the plunger but change the needle;
 - 10. Perform the injection;
 - 11. Record in the CRF the volume injected;
 - 12. Replace the used siringe in the box (without needle);
 - 13. Store in a safe place for future check.

Repeat the procedure for the LEFT side of the face.

Warnings: Do not use product after the expiry date. Do not use the product if the primary package is not intact or damaged. Do not use the product if it does not appear to be in normal condition. The siringes are disposable and CANNOT BE RESTERILISED; once the package has been opened, the material must be used immediately. Do not mix the medical devices with other substances. Do not place in contact the devices with quaternary ammonium salts as benzalkonium chloride. Do not inject any type of drug into the gel.

- Pain assessment. After implantation, participants will remain in a medical room for at least 60 minutes to be assessed for possible adverse events and for the pain. Pain will be assessed by the Blind Evaluator immediately (within 1 min) after the last injection and later after 15-30-45-60 min. by means of a 100-mm Visual Analogic Scale (VAS) (see paragraph 7), separately for each side.
- Adverse events will be monitored throughout the duration of the study (from obtainment of Informed consent to end of the study) and recorded in the subject's medical records and in the appropriate section of the CRF;
- An appointment will be taken for the next visit, scheduled after 2 weeks (\pm 2 days).

Visit 2 (week 2 ± 2 days): follow-up visit

The following assessments and procedures will be performed during Visit 2:

- All concomitant medications being taken by the subject will be checked and, in case of changes from the previous visit, will be recorded in the subject's medical records and in the appropriate section of the CRF;
- Vital signs (blood pressure and heart rate) will be measured and recorded;
- The occurrence of adverse events from the previous visit will be checked and (if any) and recorded in the subject's medical records and in the appropriate section of the CRF;
- The GAIS scale will be admnistered;
- The digital photo will be done;
- An appointment will be taken for the next visit, scheduled after 12 weeks from Visit 1.

Visit 3 (week 12 ± 10 days): follow-up visit

The following assessments and procedures will be performed during Visit 3:

- All concomitant medications being taken by the subject will be checked and, in case of changes from the previous visit, will be recorded in the subject's medical records and in the appropriate section of the CRF;
- Vital signs (blood pressure and heart rate) will be measured and recorded;
- The occurrence of adverse events from the previous visit will be checked and (if any) and recorded in the subject's medical records and in the appropriate section of the CRF;
- The GAIS scale will be admnistered;
- The WSRS will be done;
- The digital photo will be done;
- An appointment will be taken for the next visit, scheduled after 24 weeks from Visit 1.

Visit 4 (week 24 ± 10 days): final visit

The following assessments and procedures will be performed during Visit 4:

- All concomitant medications being taken by the subject will be checked and, in case of changes from the previous visit, will be recorded in the subject's medical records and in the appropriate section of the CRF;
- Vital signs (blood pressure and heart rate) will be measured and recorded;
- The occurrence of adverse events from the previous visit will be checked and (if any) and recorded in the subject's medical records and in the appropriate section of the CRF;
- The GAIS scale will be admnistered;
- The WSRS scale will be done
- The digital photo will be done;
- The general satisfaction assessment concerning the results of treatment will be done both the Blind investigator and by subject .

Early termination visit

In case of premature withdrawal from the investigation during the follow-up period for whatever reason, all efforts should be made to perform an 'Early termination Visit, which will include all available assessments as described above for Visit 4 (Final visit). The Investigator will duly record the reason for premature withdrawal in the subject's medical records and in the appropriate section of the CRF.

Visit 4, or the 'Early termination Visit', will represent the conclusion of subject's participation in the investigation.

6.2 Subject withdrawals

Subjects have the right to withdraw from the investigation at any time for any reason including personal reasons (consent withdrawal).

The Investigator also has the right to withdraw any subject from the investigation if he/she deems this appropriate and in the best interest of the subjects.

The following necessitate the discontinuation of a subject from the investigation:

- Protocol violation: at least one of the conditions that represent any of the exclusion criteria occurred at any time during the investigation;
- Lack of efficacy of the product: the appearance of the face will worsen during the follow-up and an alternative treatment is required;
- Voluntary subject withdrawal for any reason (consent withdrawal);
- If an adverse event (including a concomitant illness) develops, which is considered by the Investigator as incompatible with the continuation of the investigation;
- If the administration of a drug which is not permitted is necessary;
- Failure to comply with the requirements of the protocol;
- The Investigator considers the investigation discontinuation as appropriate, in the best interest for the subject;

• Subject dies during the investigation: the reason and the date of death will have to be recorded in the medical records and in the CRF, together with the Investigator's opinion on the correlation between the cause of death and the investigational medical device.

In case of withdrawal from the investigation, the reason and the date of discontinuation must be recorded in the medical records and in the CRF.

It is understood by all concerned that an excessive rate of withdrawals can render the investigation un-interpretable, therefore unnecessary withdrawals of subjects should be avoided. However, should a subject decide to withdraw, all efforts will be made to complete and report the observations as throughly as possible. A complete final evaluation at the time of the withdrawal (investigation end-point) should be performed in the 'Early termination Visit', and a clear, univocal explanation of the reason why the subject is withdrawn from the investigation should be reported.

Subjects prematurely withdrawn from the investigation during the follow-up period will not be replaced. They will undergo a final examination according to the procedure described for the Final Visit.

6.3 Early termination of the investigation

Both the Sponsor and the Investigator reserve the right to terminate the investigation at any time.

The Sponsor has the right to terminate the entire investigation at any time, for any reason, including but not limited to the following:

- Uprising of unexpected, significant, or unacceptable risk to subjects;
- The information on the investigational medical device leads to doubt as to the benefit/risk ratio;
- Subject enrolment is unsatisfactory and the subject recruitment lags behind the prospected timetable by more than 50%;
- The Investigator has received from the Sponsor all investigational medical device, means and information necessary to perform the clinical investigation but has not included any subject after a reasonable period of time mutually agreed upon;
- Non-compliance of the Investigator or Sub-investigators, delegated staff with any provision of the clinical investigation protocol, and breach of the applicable laws. In any case the Sponsor will notify the Investigator of its decision by written notice.

The Investigator may terminate the participation in the investigation if the investigational site for any reason becomes unable to perform or complete the clinical investigation.

Should the early termination of the investigation be necessary, the procedures for an early termination or temporary halt will be arranged after consultation by all parties involved. The Sponsor should submit a written notification to the competent authority concerned and the independent ethic committee (IEC), providing the justification of premature ending or of the temporary halt.

7. ASSESSMENT OF PERFORMANCE

The following performance parameters will be evaluated in the investigation:

Primary endpoint

The primary performance endpoint of this investigation will be the pain severity experienced by subjects during and immediately after injections (recording times: within 1 min and 15-30-45-60 minutes after the last injection).

Secondary endpoint

The secondary performance endpoint of this investigation will be to assess and compare the efficacy of HAL and of HA injection.

Methods of assessment

Pain severity

Pain severity associated with injection will be measured within 1 min and 15-30-45-60 minutes after the injection, separately for each site (right/left), using a 100-mm Visual Analogue Scale (VAS).

The VAS is a measurement instrument that tries to measure the amount of pain that a subject feels, that ranges across a continuum from none to an extreme amount of pain.

Operationally a VAS is usually a horizontal line (sample below), 100 mm in length, anchored by word descriptors at each end, where the left extreme mean "No pain = 0" while the right extreme means "Worst Pain Imaginable = 100".

Subjects will mark on the line the point that they feel representing their perceived pain.

The VAS score is the distance (in millimetres) from the left end of the line to the point where the subject's mark crossed the line. The measurement will be conducted by the same person at each visit.

Notice: the mark on the line shoud be a vertical stroke [] *not a cross* [x].

Ten VAS forms will be provided for each subject (two forms –left and right side- for each of the five recording times), attached but not included in the CRF.

Clinical efficacy: subjective evaluation

The aesthetic results of the treatment will be evaluated by the subject, separately for each site (right/left), 2, 12 and 24 weeks after treatment. Evaluation will be done by means of the Global Aesthetic Improvement Scale (GAIS), based on five scores referred to the pre-treatment state:

GAIS

score	definition	
very much improved	excellent corrective results	
much improved	marked improvement of the appearance, but not optimal	
improved	improvemente of the appearance, better compared with the initial condition, but a touch-up is advised	
no change	the appearance substantially remains unchanged in respect of the original condition	
worse	the appearance worsened compared with the initial condition	

Six GAIS forms will be provided for each subject, attached but not included in the CRF.

Clinical efficacy: objective evaluation

The aesthetic results of the treatment will be evaluated by the blind investigator, separately for each site (right/left), by means of the Wrinkle Severity Rating Scale (WSRS)⁴³, based on five scores, done before the treatment and a the weeks 12 and 24:

grade	wrinkle	description
1	absent	no visible nasolabial fold; continuous skin line
2	mild	shallow but visible nasolabial fold with a slight indentation; minor facial feature; implant is expected to produce a slight improvement in appearance
3	moderate	moderately deep nasolabial fold; clear facial feature visible at normal appearance but not when stretched; excellent correction is expected from injectable implant
4	severe	very long and deep nasolabial fold; prominent facial feature; <2 mm visible fold when stretched; significant improvement is expected from injectable implant
5	extreme	extremely deep and long nasolabial fold, detrimental to facial appearance; 2–4 mm visible V-shaped fold when stretched; unlikely to have satisfactory correction with injectable implant alone

The WSRS score will be entered directly in the CRF by the blinded evaluator.

At the final visit both the blind investigator and the subject will express a global satisfaction assessment (GSA) on corrective procedure (for each side of the face):

Global satisfaction assessment	(GSA)) scale
--------------------------------	-------	---------

unsatisfying	satisfying	very satisfying
0	1	2

⁴³ Day DJ, Littler CM, Swift RW et al . *The Wrinkle Severity Rating Scale. A validation study*. Am J Clin Dermatol 2004; 5 (1):49-52

Clinical efficacy: objective recording

Immediately before treatment, after treatment (within 1 hour) and at all follow-up visits (V2-V3-V4) a digital picture of the face will be taken.

The photo will be taken from a frontal point of view according to the standard procedures of the study site (sitting position of the subject; soft environmental daylight; neutral uniform background; digital camera; distance subjects camera 1,2-2.0 m; focal lenght adjusted to 70-90 mm [35 mm format equivalent]; neutral white balance; automatic ISO exposure).

As soon as possible the digital file will be copied in a PC: for each photo almost the date of the shot and the subject number will must available. A separate backup of the files is advisable.

The digital files shoul be password-protect; the access will be permitted only to the Principal Investigator and to selected Co-Investigator(s).

Files must be recorded, stored, handled and protected according to the ICH and (UE) 2016/679 rules (privacy law)

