3. INVESTIGATION DESIGN

This will be a pre-CE mark controlled, prospective, randomized, blinded evaluator, single centre, split-face clinical investigation.

Each subject will receive both medical devices under investigation, one (HAL) on the one side of the face, the other (HA) on the other side, in randomized fashion.

The products will be administered by the Investigator/Co-Investigator (Treating Investigator), while the evaluations will be done by a Co-Investigator not aware of the side type treatment (Blinded Evaluator).

The investigational plan include a Visit 1, during which subjects will be screened for entry (inclusion/exclusion) criteria; eligible subjects will be treated with the medical devices and followed for the next hour for pain and safety evaluation.

Visit 2, 3 and Visit 4 are schedule after 2 (\pm 2 days), 12 (\pm 10 days) e 24 (\pm 10 days) weeks for the assessment of safety and clinical efficacy.

Subjects prematurely discontinued from the investigation after the treatment will perform an 'Early termination visit', in which procedures scheduled for Visit 4 (24 weeks, final visit) will be performed (whenever feasible). In case of premature discontinuation of the investigation, the Investigator will duly record the reason for premature withdrawal in the appropriate section of the case report form (CRF).

Visit 4 (or the 'Early termination Visit') will represent the conclusion of subject's participation in the investigation.

Adverse events will be recorded during the entire investigational period by investigator's assessment and subjects' spontaneous reporting. Vital signs (blood pressure and heart rate) will be measured at each visit in the investigational site.

The total duration of the investigation for each subject will be 24 weeks. This time frame has been selected basing on literature data related to dermal fillers based on hyaluronic acid.

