5.3 Packaging and labelling

The labelling of the investigational product will be performed in accordance with the ISO 14155 guideline for medical devices and all local requirements.

Each single box will be labelled with almost the following information:

- clinical investigational plan code, sponsor's references,
- study site identification,
- Principal Investigator's name,
- product identification,
- batch number and expiry date
- storage conditions,
- the statement 'for clinical study only',
- the statement 'keep out from children',
- place to write the subject code,
- place to write the administration date .

Example:

	Clinical Trial HA28L/MD01/20		
Matex Lab Switzerland SA,[name]			
[contact]			
Study site	Clinica Dermatologica, Dipartimento di Medicina Clinica e Sperimentale		
	Azienda Ospedaliera Universitaria Pisana		
	[name]		
Principal Investigator	[name]		
Product	(HA or HAL)		
batch number/expiry date	XXX/XXXX*		
	Subject n°		
Da	te of admnistration		
For clinical study only. Keep store of	out from children . Protect from damage, freezing and sunlight; at a temperature between + 4° C and 27°		

Each siringe will be labelled almost with the product identification, the study code and a place to write the subject code.

An autoadesive flag label reporting the same data (to be sticked on CRF) is foreseen.

The Investigator and/or Hospital Pharmacist will be responsible for the correct storage and distribution of the investigational medical device, as well as of its accountability.

The Sponsor of the investigation will be responsible for the investigational medical device shipment to the Hospital Pharmacy.

An adequate amount of investigational devices will be supplied to the investigational site. Reserve units will be supplied in case of damaging of the scheduled units.

At the end of the investigation, following a final reconciliation on products accountability, both the used and the unused investigational medical devices will be sent to the Sponsor or locally destroyed at the investigational study site according to the local standard operating procedures (SOPs).

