10.1 Data management

10.1.1 Case report form (CRF)

The data generated in this investigation will be recorded at the investigational site by the appointed investigation personnel on an investigation-specific CRF.

A paper CRF will be designed to record all the protocol-required information to be reported to the sponsor. The main purpose of the CRF is to obtain data required by the clinical investigation protocol in a complete, accurate, legible, and timely manner.

All subjects' data, recorded in the CRF by the Investigator and/or his/her designee, will have to find source in the source documents (e.g., subject's medical records).

The CRF should be filled-in during or immediately after the conclusion of each visit, preferably within 24 hours but no later than five working days after the visit.

No blank sections or unanswered questions should appear in the CRF: in the case that the requested information cannot be provided, the statement "NAV" (not available) or "ND" (not detected) should apply specifying the reason or "NA" (not applicable) if not pertinent; in the section "notes/observations the statement "none" or "NOR" (nothing of relevance) or a cross line should apply when there is no need to provide further information.

The completion of the CRFs will be done using an indelible writing possibly in black colour (use a ball pen, not a fountain pen). Possible changes or additions to data already reported in the CRF should be performed using an indelible writing, possibly in black colour, dated and initialled by the person who performs changes. The reason of change/addition should be explained. In the case of correction, the original data should not be modified but erossed in order that the original version remains legible and verifiable. In no circumstances erasures or masks of the original data with masking fluids should appear.

The forms of the CRFs will be produced in a self-copying paper in thrice copy, one white (original, to be withdrawn by the sponsor) and two coloured copies (one to be sent to the statistician and another to be stored in the site documentation).

In the event that the CRF section dedicated to the recording of adverse events is not sufficient for the completion of recordings, a photocopy of the blank CRF can be used: in this case the original copy will be withdrawn by the monitor and 2 photocopy will be attached and punched to the corresponding CRF.

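### The evaluator scores WSRS in the same CRF that carries each side's HA/HAL label, and the available text does not say whether the subject marking the primary pain VAS is masked

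*Combined protocol and SAP*

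**What the plan says.** **Evaluator.** Section 3 has the Treating Investigator inject, "while the evaluations will be done by a Co-Investigator not aware of the side type treatment (Blinded Evaluator". Section 5.3 provides for the label: "An autoadesive flag label reporting the same data (to be sticked on CRF) is foreseen". The specimen box label in that section has a product line to be filled with HA or HAL. At Visit 1, step 5 of the treatment procedure in section 6.1 reads "Detach the flag label and stick it on the appropriate space present in the CRF". If the label is missing, a witness writes the product code in that space instead. The procedure is then repeated for the left side. Section 7, on the objective evaluation of efficacy, says "The WSRS score will be entered directly in the CRF by the blinded evaluator", with ratings before treatment and at weeks 12 and 24.

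Section 10.1.1 describes a self-copying paper CRF in three copies, "one white (original, to be withdrawn by the sponsor) and two coloured copies". One coloured copy goes to the statistician and "another to be stored in the site documentation". When the white copy is withdrawn is not stated.

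**Subject.** Under section 7 the subject marks the VAS line, separately for each side. Section 5.3 says of the syringe: "Each siringe will be labelled almost with the product identification, the study code and a place to write the subject code". Sections 3 and 6.1 contain no statement that the subject is masked and no step that hides the label or the side allocation. The summary and section 3 describe the trial as evaluator-blinded only.

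**The concern.** There are two separate routes, and they bear on different endpoints.

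The first concerns the WSRS, a secondary endpoint. To enter a week 12 or week 24 score, the evaluator has to handle the document that holds the treatment code for each side. If both sit in the same open booklet, the blind depends on the evaluator not turning a page. The direction of any resulting bias is unclear, because section 1.2 expects equal aesthetic results with and without lidocaine.

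The second matters more for the trial's conclusion. The primary endpoint is self-rated pain, so blinding the evaluator who runs the assessment does not protect it. Section 1.2 reports less pain with lidocaine-containing fillers. A subject who knows the HAL side and shares that expectation may score that side lower. In a split-face design the expectation would follow treatment exactly, side by side. Randomizing the side does not remove it, and the paired t-test in section 10.2.5 would count it as a device effect.

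**Working it through.** **1. Which assessments can the CRF route reach?**

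| Assessment | Where recorded | Reached by the label in the CRF? |
|---|---|---|
| WSRS, baseline | CRF | No: listed before treatment in section 6.1, so before the label is placed |
| WSRS, weeks 12 and 24 | CRF, by the blinded evaluator | Possible |
| Pain VAS | Forms kept outside the CRF (section 7) | No |
| GAIS | Forms kept outside the CRF (section 7) | No |
| Global satisfaction, week 24 | Not stated | Not counted |

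The route can therefore touch at most 2 of the 3 scheduled WSRS assessments.

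**2. Is a safeguard described?** Section 10.1.1 asks for named CRF handlers and locked archiving. Neither separates the evaluator from the treatment entries, because the evaluator must write in the CRF. No separate or sealed treatment page is described. The CRF layout is not part of the documents.

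**3. Subject route.** Product identity is on box and syringe (section 5.3), and the subject produces the score (section 7). The available text describes no masking step. It also does not show that a subject sees or understands the label, or is told the side.

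**4. What would a given expectation bias do to the primary test?** Inputs from section 10.2.1: n = 52, SD of paired differences 2.5, two-sided alpha 0.05, difference to detect 1.0 (unit not named). Each side yields one time-averaged VAS score, so there are 52 paired differences.

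- SE = 2.5/√52 = 0.3467
- Critical value t(0.975, 51) = 2.0076
- Smallest significant mean difference = 2.0076 × 0.3467 = 0.696

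The plan's own figure first: a true difference of 1.0 has noncentrality 1.0/0.3467 = 2.88, and the noncentral t with 51 df gives power 0.808. This matches the stated 81%.

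Now set the true device effect to zero and assume a mean bias b in favour of HAL. The noncentrality is b/0.3467, and the table gives the probability of a significant result favouring HAL (upper tail only):

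| Assumed bias b | b/SD | Noncentrality | Significant in favour of HAL |
|---|---|---|---|
| 0 | 0 | 0 | 2.5% |
| 0.10 | 0.04 | 0.29 | 4.7% |
| 0.25 | 0.10 | 0.72 | 10.5% |
| 0.50 | 0.20 | 1.44 | 29.3% |
| 0.70 | 0.28 | 2.02 | 50.8% |

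The values of b are assumptions, and nothing in the documents supports any one of them. The table shows how sensitive the test is to such a bias and does not estimate one.

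**The case against.** The strongest reply is that nothing here shows a broken blind. The space for the label may be on a page kept apart from the follow-up pages, and section 3 already obliges the evaluator to be unaware of treatment. Page separation could be left to CRF design. For the subject, what is said about side allocation would naturally be in the information sheet, which is not in the text available. Section 1.2 is the sponsor's rationale and is not shown to be given to subjects. Used syringes go back into the box and into safe storage (section 6.1, steps 12 and 13), and section 5.7 restricts access to device stock. The rejection rates are simply the plan's power curve read at assumed biases.

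Most of this stands as a limit on the claim. A reader might infer that the evaluator will be unblinded, that subjects will know their HAL side, or that the protocol contradicts itself on subject masking. The documents support none of these: the CRF layout is unknown, disclosure to subjects is unknown, and subject masking is never claimed.

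The reply does not close the gap. The protocol does specify where the code goes, what it shows and where the evaluator writes, and those instructions together leave the route open. Steps 12 and 13 come after the injection and are not presented as blinding measures. Section 6.1 also has the Blind Evaluator start the pain assessment within a minute of the last injection, when labelled boxes and syringes may still be nearby.

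**Conclusion.** The point holds as a cheap improvement that should be made. As written, the procedures put each side's treatment code in the CRF that the blinded evaluator uses for the week 12 and 24 WSRS, with no described separation. In the available text, the self-rated primary endpoint has no stated masking of the subject. The first is a possible exposure affecting at most two WSRS assessments. The second is an omission that leaves a bias route open on the primary comparison.

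The size of any bias is unknown. The range of 4.7% to 50.8% rests on assumed mean biases of 0.10 to 0.70, no true device effect, and the plan's n = 52 and SD of 2.5. It should not be read as a forecast of the false-positive rate or as a finding that the primary result would be invalid.

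**What to change.** 1. Change step 5 of the Visit 1 procedure (section 6.1) and the flag-label sentence in section 5.3 so that flag labels and per-side product codes go into a separate treatment log. The Treating Investigator or pharmacist holds the log, and the Blinded Evaluator has no access until database lock. State that it stays open to the monitor (section 11), device accountability (section 5.7) and safety reporting (section 9).
2. Keep boxes and syringes out of the subject's and evaluator's view, and cover the product name once the Treating Investigator has chosen the box under steps 1 and 2, so that those steps can stay as they are. State that the subject is not told the side allocation. Section 5.1 describes both gels as transparent and colourless, so this looks feasible.
3. If the subject is not to be masked, say so and name it as a limitation of the primary endpoint.

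Masking of the subject cannot be guaranteed, because numbness from lidocaine may itself reveal the side; the report should acknowledge this.

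**Cost.** No extra visits, staff or subjects. There is a second accountability document to keep, and covered labels must be checked against section 5.3: "The labelling of the investigational product will be performed in accordance with the ISO 14155 guideline for medical devices and all local requirements". If the amendment is substantial, section 13.5 requires new ethics committee approval before it is implemented.
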